3.2 Primary Study Endpoints

The primary endpoint is the proportion of subjects who tolerate at least 1043 mg cumulative of peanut protein with no more than mild symptoms at the 12 month DBPCFC

3.3 Secondary Study Endpoints

The secondary endpoints are as follows:

- To determine the proportion of subjects who experience dose related GI side effects during oral immunotherapy

CONFIDENTIAL

This material is the property of the University of Chicago.
Do not disclose or use except as authorized in writing by the study PI

05.16.2023

- To determine the proportion of subjects who experience hypersensitivity reactions (other than GI) during oral immunotherapy

The exploratory endpoints are as follows:

- To demonstrate the effect of resistant potato starch (RPS) on the fecal microbiome and metabolome
- To determine if gnotobiotic mice colonized with the fecal microbiota of study participants models clinical response
- To evaluate the immunological effects of fiber supplementation in children
 - Change in peanut specific IgE and IgG4 levels
 - Change in peanut skin prick test mean wheal diameter
 - Change in peanut component levels

4 Subject Selection and Withdrawal

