Unfortunately, OIT is an imperfect therapy as >70% of children undergoing therapy experience gastrointestinal (GI) side effects, including eosinophilic esophagitis, which has led to a significant drop out rate in clinical trials. In addition, a high rate of systemic allergic reactions, that were treated with epinephrine, have been seen in study populations.⁴ Finally, little evidence exists to support using OIT as a cure for or to induce remission of peanut allergy, nor does evidence exist that supports the ability of children to “free eat” peanut in their diet after completion of therapy. As a result, children must continue to take a daily dose of peanut protein for the rest of their lives in order to remain bite safe without expectation of any other benefit.⁷

One barrier to the development of a more effective therapy is the lack of understanding of the pathogenesis of this disease. The rate of increase in peanut allergy is too high to be explained by genetics alone. A theory that may, however, explain both the development and increasing prevalence of peanut allergy is the “microbiome hypothesis” which posits that commensal microbes or “good bacteria” in our gastrointestinal (GI) tract interact with our immune system through production of short chain fatty acids (SCFA), including butyrate, after digestion of dietary fibers. In turn, butyrate acts as a “postbiotic” that influences both the development and severity of chronic non-infectious inflammatory diseases such as food allergy.⁸⁻¹⁰

This hypothesis is supported by the vast changes in the modern lifestyle that may impact colonization of commensal microbes in our GI tract, including diet, antibiotic use, antiseptic use, food sterilization, smaller family sizes, and reduced exposure to farm animals. The American diet is largely devoid of fibrous fruits and vegetables that act as prebiotic “food” for our commensal bacterial and instead high in processed sugars which favor growth of non-SCFA producing bacterial species. Both antibiotics and external antiseptic use have been shown to influence the GI microbiome, including antibiotics fed to livestock later

CONFIDENTIAL

This material is the property of the University of Chicago.
Do not disclose or use except as authorized in writing by the study PI

05.16.2023

sacrificed for meat. Finally, the colonization or recolonization of commensal bacteria has likely been affected by the lack of exposure to bacteria in our day to day life.¹¹

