In this study, we are enrolling subjects between the ages of 4 and 17, inclusive with peanut allergy and asking them to consume either a RPS or a control starch (corn starch). This consumption of either product may increase the overall caloric intake of subjects which may lead to weight gain. Subjects in the RPS group will be asked to consume 1 tablespoon (12 grams) of a fiber supplement daily which contains 40 calories/tablespoon. Subjects in the control group will be asked to consume 1 tablespoon (8 grams) of ACS daily which contains 30 calories/tablespoon. In addition, an increase in fiber consumption may lead to bloating, gas and/or constipation.

Risks Associated with DBPCFC

In this study DBPCFCs will be conducted in accordance with the recommended PRACTALL guidelines. The screening DBPCFC is utilized as the standard of care to confirm peanut allergy and does not confer higher than minimal risk than a open label food challenge used clinically to confirm peanut allergy prior to POIT. The screening DBPCFC will also establish a threshold for reactivity for comparison with the exit DBPCFC. The exit DBPCFC will be used to establish efficacy of POIT and confirm safety of accidental ingestion of peanut. The exit DBPCFC also does not confer more than minimal risk above a standard of care open label food challenge used during POIT to confirm tolerance of peanut ingestion. DBPCFC are expected to induce allergic reactions. Reactions range from mild (nausea, few hives) to severe (wheezing, diffuse urticaria, rhinitis/conjunctivitis, vomiting/diarrhea, impending doom) to potentially life threatening (low blood pressure, difficulty breathing, neurologic changes). Administered in a controlled setting under the supervision of experienced staff, food challenges are considered safe and are the

CONFIDENTIAL

current gold standard for the diagnosis of peanut allergy. As soon as symptoms consistent with an allergic reaction are witnessed, interventions to stop the reaction are begun (H1 antihistamines and epinephrine).

Risks Associated with POIT

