The most common side effect associated with POIT is GI symptoms, including stomach pain and mouth itching. These are expected to occur in nearly 2/3 of individuals. These symptoms tend to be transient in nature and typically occur in the first few days after up-dosing POIT and for the first hour after taking the dose. GI symptoms are mitigated by eating large meal with each dose and staying well hydrated. Symptoms will be controlled with H1-antihistamines as needed. Systemic allergic reactions/anaphylaxis is also a side effect of POIT. This risk is mitigated by restricting physical activity, hot showers, and NSAID use for 3 hours after daily dosing of POIT. Should symptoms occur, they will be treated with epinephrine. All participants will be required to carry an epinephrine autoinjector. POIT may also be associated with eosinophilic esophagitis. The reported incident is <1% and typically resolves with removal of peanut protein exposure.

Risks Associated with Blood Draw

All subjects enrolled in the study will be asked to undergo a blood draw. The risks involved in drawing blood from a vein may include, but are not limited to, momentary discomfort at the site of the blood draw, possible bruising, redness, and swelling round the site, bleeding at the site, feeling of lightheadedness when the blood is drawn, and rarely, an infection at the site of the blood draw. In order to minimize these risks, blood draws will be done under hygienic conditions by experienced personnel.

Potential benefits of Prebiotic Fiber

The potential benefits of consuming a fiber supplement include reducing constipation, maintaining a healthy weight, lower blood sugar and cholesterol levels. The theoretic benefit to consuming a fiber supplement is that it may improve tolerance of oral immunotherapy to peanut and/or improve immunologic markers associated with peanut allergy. No additional benefit is hypothesized from the control fiber.

Benefits of Oral Immunotherapy (OIT)

The benefit of undergoing peanut OIT is that subjects become “bite-safe” in case of an accidental ingestion of peanut protecting them from a severe, systemic allergic reaction.

2 Study Objectives

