2.1 Primary Objective

The primary objective of this study is to determine if prebiotic therapy improves outcomes and reduces side effects associated with POIT.

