6.7 Visits 16 and 17 (3 months after visit 15)

- Interval medical history (visit 16 only)
- Vital signs
- Physical examination, including height and weight
- Stool sample collection (visit 16 only)
- Skin prick test (visit 16 only)
- Blood draw (visit 16 only)
- Spirometry (if has asthma diagnosis; as COVID allows)
- DBPCFC

7 Statistical Plan

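### The only GI side-effect endpoint is ever/never at an expected rate of about 67% to over 70%, so it responds weakly to fewer symptomatic doses; separately, no log hand-in is listed after Visit 15

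*Combined protocol and SAP*

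**What the plan says.** The primary objective (2.1) is to "determine if prebiotic therapy improves outcomes and reduces side effects associated with POIT". The GI part is carried by one secondary endpoint in 3.3: "To determine the proportion of subjects who experience dose related GI side effects during oral immunotherapy". The companion endpoint for non-GI hypersensitivity reactions has the same form. Section 7.2 compares categorical variables by chi-square or a non-parametric equivalent. No count, rate, severity or duration measure is named, and 3.3 does not define what makes a symptom dose related.

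The expected frequency appears twice. Section 1.1 says "OIT is an imperfect therapy as >70% of children undergoing therapy experience gastrointestinal (GI) side effects". Section 1.5 says of GI symptoms, "These are expected to occur in nearly 2/3 of individuals", and that they "typically occur in the first few days after up-dosing POIT and for the first hour after taking the dose". On the starch, 1.5 also says "an increase in fiber consumption may lead to bloating, gas and/or constipation".

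The sample is 30 children (7.1), randomized 1:1 (Study Summary). No alpha, sidedness or power is stated.

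The Schedule of Procedures has a row for dosing and AE logs. Read with 6.3, 6.5 and 6.6, its marks fall at Visit 4, Visits 6–14 and Visit 15. The list for Visits 16 and 17 in 6.7 has no log item. It does have an interval history at Visit 16, and 8.2 has the investigator ask about adverse effects at every contact.

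**The concern.** An ever/never measure is used up by a child's first symptom. Section 1.5 describes GI symptoms as transient and tied to up-dosing, and 3.1 sets out many up-dosing steps, so most children can be expected to have at least one. If the starch makes symptoms rarer without removing them altogether, most of that benefit does not reach the endpoint. What is at stake is half of the primary objective, and the effect estimate that a pilot should pass on to a larger trial.

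The endpoint also takes no account of how many POIT doses a child took, and does not separate symptoms near the POIT dose from symptoms of the starch taken daily alongside it.

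The log gap is a different matter. A per-dose measure needs the diary to the end of maintenance, and no visit is listed at which the last part is handed in.

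**Working it through.** The plan states no power or effect size, so there is no figure to reproduce.

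**Inputs from the documents.** 30/2 = 15 per arm; control rate 2/3 (1.5) or 70% (1.1); chi-square or equivalent (7.2).

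**Assumptions.** Two-sided 0.05, no dropout, and the episode distributions below. The documents give none of these. Ever/never powers come from exact enumeration of all 16 × 16 outcomes; count powers are simulated.

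**Step 1. What halving the burden does to ever/never.**
- (a) The proportion itself halves: 70% to 35%.
- (b) A Poisson episode rate halves: λ = −ln(1 − 0.70) = 1.204, so the new proportion is 1 − exp(−0.602) = 45%.
- (c) A negative binomial mean halves: P(any) = 1 − (1 + μ/k)^−k. With k = 0.5, P = 70% needs μ = 5.06. At μ/2 = 2.53, P = 1 − 6.06^−0.5 = 59%. At μ/3 = 1.69, P = 52%.
- (d) The same children are affected, with half the episodes: 70% v 70%.

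**Step 2. Power at 15 per arm.**

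| Scenario | Ever affected | Chi-square | Fisher |
|---|---|---|---|
| (a) proportion halves | 70% v 35% | 48% | 32% |
| (a) proportion halves | 67% v 33% | 44% | 29% |
| (b) Poisson rate halves | 70% v 45% | 27% | 15% |
| (b) Poisson rate halves | 67% v 42% | 26% | 14% |
| (c) k = 0.5, mean halves | 70% v 59% | 10% | 4% |
| (c) k = 0.5, two-thirds cut | 70% v 52% | 17% | 8% |
| (d) same children, half the episodes | 70% v 70% | 5.5% | 1.7% |

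Row (d) is the false-positive rate. In (c), fixing 70% ever affected and varying the control mean from 2 to 40 episodes moves chi-square power for a halving from 17% to 6%. At 70% the expected number of unaffected children per arm is 15 × 0.30 = 4.5, so the Fisher column may be the relevant one if the fallback in 7.2 is read as Fisher's test. For 80% power from 70%, the RPS rate would have to fall to about 20% (chi-square) or 14% (Fisher).

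**Step 3. Counts on the same data (70% ever affected, k = 0.5).** Wilcoxon, and t on log(1 + count), give about 16–18% for a halving (14–19% over repeat runs) and 31–37% for a two-thirds cut (30–37% over repeat runs). A negative binomial likelihood-ratio test, with equal exposure, gives about 25% for a halving and 49% for a two-thirds cut. Its false-positive rate at this size is about 6.5% rather than 5%, so part of that gain is not real.

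**Step 4. Other spreads for a burden measure, true halving.** If every child has some symptoms, power is 97%, 77%, 48% and 33% for a between-child SD of log rate of 0.5, 0.7, 1.0 and 1.25. If 20–30% have none and the same children stay affected, Mann-Whitney power is about 15–54% for SDs of 0.5 to 1.0.

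**Step 5. The log gap.** The schedule puts Visit 14 at about M8, Visit 15 at M11 and Visit 16 at M14. The stretch without a hand-in is 14 − 11 = 3 months: half of the six months of maintenance, or 3/14 = 21% of the time since POIT began. If risk were constant and nothing else captured late events, a true ever-rate of 70% would be seen as 1 − 0.30^(9/12) = 59% (12 months of POIT, as the text has it) or 1 − 0.30^(11/14) = 61% (14 months, as the schedule has it). That is a worst case, because 1.5 ties symptoms to up-dosing, which is over by then.

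**The case against.** The best defence is that the study is an exploratory pilot of 30 children (7.1), that a proportion matches how both background rates are expressed, and that sample size is the main limit whichever measure is used. This largely stands. Step 3 shows that a count analysis would still miss a true halving about three times in four or more in that scenario. It argues for adding a burden measure, not for replacing the endpoint mid-trial.

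A reader might infer several stronger things that the documents do not support:

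- *A halving would be invisible.* That is so only if the same children stay affected, or nearly so if episodes cluster strongly. Rows (a) and (b) show 26–48% chi-square power under other readings.
- *The last three months of logs are lost, and this hides the effect.* The documents show only that no hand-in is listed. Section 8.2 questioning and the Visit 16 interval history remain, and 5.4 keeps a daily diary of medication for side effects. The gap falls after up-dosing and applies to both arms, so it does not cause the insensitivity.
- *The endpoint favours the arm with more early stopping.* No differential stopping is shown, and 1.1 links dropout to GI effects, so many early stoppers would already count as events.
- *Starch symptoms will be charged to POIT in the RPS arm.* This is possible, since dose related is undefined. But the term is there, and 8.2 has the investigator assess each event's association with study treatment. The direction is not established.

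A per-dose rate has its own weakness. Risk is concentrated after up-dosing, so one rate over all doses dilutes completers with low-risk maintenance doses. Section 1.5 gives the first hour as typical only, so a hard one-hour cut could drop genuine POIT symptoms, and nothing says that the diaries record onset time.

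**Conclusion.** The point holds in limited form. The one GI endpoint is ever/never at an expected rate of nearly two thirds to more than 70%. At 15 per arm it has about 5–30% chi-square power against a halving of episode frequency, and about 44–48% if the proportion affected itself halves. A count or rate analysis uses more of the information and does better in the scenarios compared, but does not give adequate power at this size under most of the spreads tried. Its value is a more informative effect estimate from data that the study already collects. All powers rest on two-sided 0.05, no dropout and assumed episode distributions.

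The absence of log collection at Visits 16 and 17 is a separate and smaller schedule omission. The documents do not support calling a benefit undetectable, calling late events uncaptured, or assigning a direction of bias.

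**What to change.** 1. Keep the proportion in 3.3 as stated. While the study team is blinded, add a pre-specified supportive burden analysis from the existing logs: POIT doses with GI symptoms per dose taken, by negative binomial regression on arm with log(doses taken) as offset. Give the rate ratio and 95% interval separately for up-dosing and maintenance, because 1.5 ties symptoms to up-dosing. Read the interval rather than the p-value, given Step 3.
2. Where onset time is recorded, tabulate GI symptoms near the POIT dose apart from other GI symptoms as a sensitivity analysis, with the 30-day starch-only period before POIT as context.
3. Do the same for non-GI reactions.
4. Add log collection at Visit 16 to the Schedule of Procedures and to 6.7.

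The cost is some diary coding and analysis, and one hand-in at an existing visit. The downsides are a supportive endpoint added mid-trial, which is why it should be fixed before unblinding, and onset time that may be missing for children already followed. Reporting by phase reduces the dilution problem but does not remove differences in exposure between early stoppers and completers.

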7.2 Statistical Methods

Chi-square testing (or non-parametric equivalent) will be used to compare categorical variables. Student's t-test (or non-parametric equivalent) will be used to compare continuous variables. Microbial relationships between samples will be compared using principal coordinate analysis and average-neighbor hierarchical clustering. Welch's t-test will be used to determine significant abundance differences between OTUs.

8 Safety and Adverse Events

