The investigator will assign severity grades to adverse events. Adverse events will be graded using the CoFAR grading system as follows:

Grade 1 (mild): transient or mild discomforts (<48 hours); no or minimal medical intervention/therapy required. For allergic reactions, these symptoms may include pruritus, swelling, or rash, abdominal discomfort or other transient symptoms.

Grade 2 (moderate): symptoms that produce mild to moderate limitation in activity that may require some assistance; no or minimal intervention/therapy is required; hospitalization is possible. For allergic reactions, these symptoms may include persistent hives, wheezing without dyspnea, abdominal discomfort/increased vomiting or other symptoms

Grade 3 (severe): marked limitation in activity that usually requires some assistance usually; medical intervention/therapy required; hospitalization is possible. For allergic reactions, symptoms may include bronchospasm with dyspnea, severe abdominal pain, throat tightness with hoarseness, transient hypotension among others. Parenteral medications are usually indicated.

Grade 4 (life-threatening): extreme limitation in activity that requires significant assistance; significant medical/therapy or intervention is required; hospitalization is probable. Symptoms may include persistent hypotension and/or hypoxia with resultant decreased level of consciousness associated with collapse and/or incontinence or other life threatening symptoms.

Grade 5 (death): death

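### The two reaction endpoints during peanut immunotherapy count any event, so a severity change would not show; name by-arm severity and epinephrine summaries and collect the Visit 16 log

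*Combined protocol and SAP*

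**What the plan says.** Part of the primary objective (section 2.1) is to "determine if prebiotic therapy improves outcomes and reduces side effects associated with POIT". Section 1.1 gives as one reason for the trial that "a high rate of systemic allergic reactions, that were treated with epinephrine, have been seen in study populations".

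Two secondary endpoints in section 3.3 cover reactions during POIT: "To determine the proportion of subjects who experience dose related GI side effects during oral immunotherapy" and "To determine the proportion of subjects who experience hypersensitivity reactions (other than GI) during oral immunotherapy". Apart from dose-relatedness for GI, they carry no qualifier. The only severity condition in any endpoint, in section 3.2, belongs to the exit food challenge and not to daily dosing.

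The analysis text in section 7.2 is generic: "Chi-square testing (or non-parametric equivalent) will be used to compare categorical variables". It names no table of grade, worst grade or epinephrine use.

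The raw material is to be recorded. Under section 8.1, "Adverse events will be graded using the CoFAR grading system as follows". Section 5.4 puts medicines taken for POIT side effects in a daily diary.

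The Schedule of Procedures marks collection of the dosing/AE log at Visit 4, Visits 6-14 and Visit 15, but not at Visit 16. Section 6.7, which lists the Visit 16 and 17 procedures, does not include log collection either.

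**The concern.** An any-event proportion gives one count to a child with brief mouth itching and one count to a child with severe abdominal pain. If RPS makes reactions milder, or more severe, without changing how many children ever have one, neither endpoint moves. The protocol expects GI symptoms to be common and mostly transient, so many children will count as affected and the information on severity within that group is discarded.

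Section 7.2 would permit a table of grades or epinephrine use. Because none is named, the choice of table and of cut-point would be made after the data are seen.

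The log is a separate matter. Both endpoints run over the whole of POIT, but the last scheduled collection of the main reaction record is Visit 15, three months before Visit 16.

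**Working it through.** **Inputs.** N = 30 (section 7.1), randomized 1:1 (Study Summary), so 15 per arm. GI rate on POIT: section 1.5 says of GI symptoms "These are expected to occur in nearly 2/3 of individuals", and section 1.1 says more than 70%. No rate is given for non-GI reactions, for graded reactions, for epinephrine use, or for the RPS arm. Section 7.1 states no power, effect size or alpha, so there is no planned figure to reproduce.

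**Expected GI count with no RPS effect on incidence.**
- 15 x 2/3 = 10.0 per arm
- 15 x 0.70 = 10.5 per arm (or more, since the text says more than 70%)

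**What the GI endpoint leaves open.** At 10/15 in each arm the risk difference is 0, with an exact 95% CI of about -33 to +33 percentage points. Among 10 affected children, the number whose worst GI reaction is Grade 2 or higher can be 0 to 10 in each arm. That is 11 x 11 = 121 combinations, all with the same endpoint result. This is true of any any-event outcome; it shows what the endpoint does not cover, not an error in it.

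**Illustration (hypothetical counts, not from the documents).** Worst GI grade:

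| | None | 1 | 2 | 3 | Any | Grade 2+ |
|---|---|---|---|---|---|---|
| Placebo | 5 | 4 | 4 | 2 | 10/15 | 6/15 |
| RPS | 5 | 9 | 1 | 0 | 10/15 | 1/15 |

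The planned endpoint shows no difference (Fisher p = 1.00). The grade table shows 40% against 7%, although even that gap has Fisher p = 0.08.

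**Precision of the added outcomes.** For one arm with x of n events, the Clopper-Pearson 95% limits are the 0.025 quantile of Beta(x, n-x+1) and the 0.975 quantile of Beta(x+1, n-x). For x = 0 the upper limit is 1 - 0.025^(1/15) = 0.218. Differences use an exact unconditional score interval, two-sided 5%, maximised over the nuisance rate. The counts below only show width.

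| Result | 95% interval |
|---|---|
| 0/15, one arm | 0 to 22% |
| 3/15, one arm | 4 to 48% |
| 10/15, one arm | 38 to 88% |
| 3/15 vs 3/15, difference | -31 to +31 points |
| 0/15 vs 3/15, difference | -46 to +3 points |

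With assumed Grade 2+ rates of 40% and 10%, Fisher's exact test at two-sided 5% would have power of about 33%. The added outcomes can therefore only be descriptive.

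**Log gap.** Visit 15 is at month 11 and Visit 16 at month 14, a gap of 3 months. Counting POIT from day 1 to month 14 gives 3/14 = 21%. Taking the Study Summary's 180 + 180 days, about 12 months, gives 3/12 = 25%. These are shares of time. Section 1.5 says GI symptoms typically follow up-dosing, and this interval is fixed-dose maintenance, so the share of events is probably smaller.

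**The case against.** The strongest reply is that this is a preference. Section 1.1 frames the problem as a high incidence of GI symptoms and systemic reactions and predicts improvement, and the two endpoints measure incidence. Nothing in the protocol predicts milder reactions at unchanged incidence, and this is an exploratory pilot of 30 children. That stands: neither endpoint is wrong, and a child in whom GI events are fully prevented would be counted correctly.

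It can also be said that section 7.2 already allows a categorical comparison of grades, and that the DSMB reviews imbalance in adverse events (section 8.4.1). The first is true but leaves the cut unspecified. The second is oversight for harm during the trial, not a reported comparison between arms.

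The Grade 1/2 boundary is soft, most of all for GI: section 8.1 places abdominal discomfort, and little or no need for treatment, under both grades. This also stands. Tabulating the full worst-grade distribution lets a reader look past the Grade 2 cut, but the table inherits the same boundary.

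On the log, Visit 16 still has interval history and concomitant-medication review, section 8.2 requires adverse-effect questioning at each contact, and diaries are source documents (section 9.2). The gap is a weakness in capture, not a loss of all late events.

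A reader might go further and infer that grade or treatment fields are missing from the case report form, because the minimum initial list in section 8.2 names neither, or that questioning covers only the fiber supplement. The documents do not support this. The case report form is not included, the list is expressly a minimum for source records, section 8.1 requires grading, and section 8.2 requires all adverse effects to be recorded.

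**Conclusion.** This is a cheap improvement to a plan whose existing endpoints are sound. As written, a change in severity among children who still react would not appear in either POIT reaction endpoint. For GI that group is about 10 to 10.5 of 15 per arm, assuming that all 15 start POIT and that RPS does not change incidence. It is a no-effect scenario, not a forecast for the RPS arm. No size is claimed for the non-GI endpoint, because the documents give no rate.

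The missing Visit 16 log collection covers about 21-25% of POIT time. It would be wrong to infer that the same share of events is lost, for the reasons given above.

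It would also be too strong to read the added summaries as a way to establish an effect: at 15 per arm they describe and cannot confirm.

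**What to change.** Keep both endpoints. Add to sections 3.3 and 7.2, as descriptive outcomes by randomized arm:

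1. Each child's worst CoFAR grade during POIT (none, 1 to 5), tabulated separately for GI and non-GI reactions, with the proportion at Grade 2 or higher for each. The split is needed because a pooled grade could hide a GI change behind a non-GI reaction in the same child.
2. The proportion with any epinephrine-treated POIT reaction. This is a reasonable marker for systemic reactions, since section 1.5 says of them "Should symptoms occur, they will be treated with epinephrine".

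Report risk differences with exact 95% CIs for the proportions and make no significance claim.

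Include all randomized children who started POIT. Count from Visit 4 to the exit food challenge or, for children without one, to their last POIT dose. The second rule matters because sections 3.1 and 8.4.3 give no exit challenge to children who stop POIT or do not complete six months at 300 mg. For a child without an exit challenge who is still dosing at Visit 16, for instance on a lower maintenance dose, end the count at that visit.

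Add dosing/AE log collection at Visit 16 to the Schedule of Procedures and section 6.7.

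The cost is endpoint and analysis wording, one table, and collecting a log at a visit that already takes place. The downsides are wide intervals, the soft Grade 1/2 boundary, and epinephrine use that depends partly on who decides to give it.
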